17.1.10.1 TLS Prophylaxis

Tumour lysis syndrome prophylaxis is mandatory for **all** patients starting 3 days before the first dose of AZD4573. TLS prophylaxis is mandatory for all infusions as outlined below in [Table 16](#), which provides TLS prophylaxis guidance that should be followed in addition to institutional guidelines. In the event of a discrepancy between the protocol guidelines for the management of TLS and the institutional guidelines of a given Investigator/centre, the Investigator should discuss with the Medical Monitor.

In addition to the criteria outlined in [Table 16](#) below, any patient with creatinine clearance (CrCL) < 80 mL/min must be considered at higher risk of developing TLS and managed appropriately.

TLS prophylaxis/management with rasburicase/allopurinol and IV fluid is permitted at any time during screening and treatment, however rasburicase and allopurinol must not be co-administered ([Howard et al 2011](#); [Howard et al 2016](#); [Jones et al 2015](#)).

Table 16 Mandatory TLS Prophylaxis Guidance (in Addition to Institutional Guidance)

Type of Cancer	Intermediate/High Risk
NHL	DLBCL OR Any LN \geq 5 cm
Prophylaxis	
Hydration ^a	Oral (1.5-2.0 L/day) plus additional IV fluid: Normal saline 500 mL over 2-4 h prior to AZD4573, then 100-175 mL/h as tolerated to maintain urine output
Antihyperuricemics	Allopurinol 300 mg orally QD beginning 3 days prior to AZD4573 and continuing at least through the end of Week 1 ^b . Consider prophylactic rasburicase ^c if baseline uric acid is elevated above ULN ^d , LDH $> 2 \times$ ULN, or high tumour burden/leukemic cells

- ^a Administer more aggressive IV fluid hydration for any patient who cannot tolerate or maintain oral hydration.
- ^b Administration of allopurinol should not be stopped at the end of Week 1, however the dose or frequency of administration may be reduced after discussion with the Medical Monitor.
- ^c The recommended dose for rasburicase is 0.20 mg/kg IV over 30 minutes. Rasburicase is contraindicated in patients with G6PD deficiency, so patients at higher risk for G6PD deficiency (eg, African or Mediterranean ancestry) should be screened for this condition prior to starting rasburicase. Rasburicase and allopurinol must not be co-administered.
- ^d Uric acid levels should be $<$ ULN before each dosing of AZD4573.

Notes: Adequate supportive therapy as per institutional guidelines should be given for all toxicities. TLS prophylaxis/management with rasburicase/allopurinol and IV fluid is permitted at any time during screening and treatment. Rasburicase and allopurinol must not be co-administered.

Abbreviations: DLBCL = diffuse large B-cell lymphoma; G6PD = glucose-6-phosphate dehydrogenase; IV = intravenous; LDH = serum lactate dehydrogenase; LN = lymph node; NHL = non-Hodgkin lymphoma; QD - once daily; TLS = tumour lysis syndrome; ULN = upper limit of normal.

Modified from [Coiffier et al 2008](#).

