Cycle 1 may also include the intra-patient ramp-up. Participants in relevant subgroups who are treated at the RP2D dose level in Part A will contribute to primary analyses along with participants from Part B.

During the 3-week dose ramp-up in the FTIH study (D8230C00001) in DLBCL participants, one event of clinical TLS was seen. The abnormal TLS laboratory results were detected at 6 hours after the start of the infusion. Based on these data, if, in the current study, a participant has no signs of laboratory TLS or clinical TLS at the 6-hour TLS monitoring assessment, the participant may leave the clinic after the collection of other laboratory samples, as per the SoA, at 7 hours after the start of the infusion and managed as an outpatient, at the discretion of the Investigator. These participants are not required to be hospitalised overnight, and must return to the clinic the next morning to complete the 24-hour TLS monitoring period as per SoA (Cycle 1 Weeks 1-3).

During the intra-patient ramp-up phase (Cycle 1, Week 1-Week 3), overnight hospitalisation is required-for participants showing signs of laboratory or clinical TLS at 6 hours after the start of the infusion must be admitted for in-patient TLS monitoring for a minimum of 24 hours after the start of the infusion and monitored every 4 to 6 hours during this time (or more frequently if clinically indicated). Sites retain the option to hospitalise participants based on clinical judgement, despite normal TLS laboratory results 6 hours after the start of the infusion.

Admission for further AZD4573 administrations is strongly recommended for participants who have experienced TLS events during the ramp-up phase. Participants who have previously experienced TLS should be admitted the night before each AZD4573 dose for TLS prophylaxis. Please refer to each study module for prophylaxis and management of TLS.

All participants will have haematology, chemistry, and urinalysis safety panels performed at Screening. Once dosing commences, all participants will be evaluated for safety, including clinical chemistry and haematology. If clinically indicated, additional clinical laboratory tests and evaluations are to be performed by the Investigator (eg, additional haematology/clinical chemistry panels, TLS parameters, liver enzyme tests); these need to be entered into the electronic case report form (eCRF).

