- ^o All participants will receive TLS prophylaxis during the intra-patient ramp up and be monitored for TLS during the first 24 hours post start of dose; this requirement will continue until they have received at least one AZD4573 dose at the target dose level (i.e., for at least the first 3 AZD4573 once-weekly doses). TLS monitoring will be performed at the following timepoints: predose AZD4573, 6 h after the start of the infusion, and 24 h (\pm 1 h) after the start of the infusion. Participants showing signs of clinical or laboratory TLS at 6 h after start of infusion must be admitted for in-patient TLS monitoring for a minimum of 24 h after the start of the infusion and monitored every 4 to 6 h during this time (or more frequently if clinically indicated). For each TLS monitoring timepoint, a TLS Monitoring page in the eCRF is to be filled out. Fluid balance must be monitored according to local institutional standards.
- ^p Urine samples will be collected at the following timepoints: Screening, Cycles 1-8, predose AZD4573 (within 72 hours prior to infusion) and within approximately 2 hours after the end of infusion, Cycles 9+ on Day 1 of each cycle, predose AZD4573 and within approximately 2 hours after the end of infusion, and at the 30-day SFU.
- ^q Pregnancy test to be performed at Screening (serum) and predose (serum or urine) on Cycle 1, Week 1, then once every 21 days (\pm 7 days) prior to initiating a new cycle and at the 30-day SFU visit. Additional testing may be performed at Investigator discretion (eg, in the event of suspected contraception failure).
- ^r Lipase and amylase should be evaluated at Screening, Cycles 1-8 predose AZD4573 (within 72 hours prior to infusion), Cycles 9+, predose AZD4573 (within 72 hours prior to infusion) on Day 1 of each cycle, and at the 30-day SFU visit.
- ^s In addition to hepatitis serology as specified, participants who are anti-HBc positive, or have a known history of HBV infection, should be monitored every 3 months with a quantitative PCR test for HBV DNA. In addition, any participants testing positive for any hepatitis serology must have PCR testing for verification purposes.
- ^t CD4, CD8, CD19, CD16/NK and serum immunoglobulins (IgA, IgM, IgG) will be drawn at Screening, Day 1 (predose) of Cycles 2, 4, 7, 9, 13, 16, 19 and every 6 months thereafter (predose), and at the 30-day SFU.

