- Grade ≥ 3 clinical TLS ([Appendix F](#)) that occurs despite protocol-recommended management will be considered a DLT.
- Laboratory TLS ([Appendix F](#)) will be considered a DLT if the metabolic abnormalities do not resolve within 5 days despite protocol-recommended management.

Note: All DLT events of TLS should be graded according to the Howard modification of the Cairo-Bishop criteria as part of TLS monitoring (Section [17.1.5](#) and [Appendix F](#)), while CTCAE grade should be applied on AE/SAE reports.

The definition of DLT excludes:

- 1 Grade 3 fatigue for ≤ 7 days after onset.
- 2 Isolated laboratory changes of any grade without clinical sequelae or clinical significance, with the exception of transaminase and bilirubin abnormalities described above.
- 3 Isolated changes in GGT (ie, with no corresponding elevation in AST, ALT, ALP, Total bilirubin or INR, and no symptoms suggestive of hepatic injury) will not be classified as a DLT.

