17.1.10.10.3 TLS Prophylaxis, Monitoring, and Management

Please refer to [Appendix F](#) for definitions of the Howard modification of Cairo-Bishop criteria for clinical and laboratory TLS.

All patients will receive TLS prophylaxis during the intra-patient ramp up and be monitored for TLS during the first 24 hours post start of dose. Monitoring for TLS includes checking potassium, calcium, phosphate, uric acid, and creatinine. Fluid balance must be monitored according to institutional standards.

Patients will be required to be monitored for TLS for up to 24 hours post dose until they have received at least one AZD4573 dose at the target dose level (ie, for at least the first 3 AZD4573 once-weekly doses). If a patient has no signs of laboratory TLS at the 6-hour TLS monitoring assessment, the patient may leave the clinic after the collection of other laboratory samples, as per the SoA, at 7 hours after the start of the infusion and managed as an outpatient, at the discretion of the Investigator. These patients must return to the clinic the next morning to complete the 24 hour TLS monitoring period as per the SoA (Cycle 1 Weeks 1-3). Patients with TLS at the 6-hour TLS monitoring assessment must be admitted for in-patient TLS monitoring for a minimum of 24 hours after the start of the infusion and monitored every 4 to 6 hours during this time (or more frequently if clinically indicated).

Sites retain the option to hospitalise patients based on clinical judgement, despite normal TLS laboratory results 6 hours after the start of the infusion. Admitting the patient for subsequent dose administrations will be done at Investigator discretion.

Any hospitalisation due to occurrence of an AE must be reported as an SAE, per definition. However, if hospitalisation is purely for the purposes of extended observation then this does not qualify as an SAE and does not need to be reported.

For all patients, results of safety laboratory testing (haematology and clinical chemistry at a minimum) must be available within 72 hours prior to dosing and must be reviewed by the Investigator prior to each administration of AZD4573.

In particular, the uric acid level must be < ULN prior to the start of each AZD4573 infusion.

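### Module 1 gives inconsistent instructions on which infusions need TLS prophylaxis and on admission after earlier TLS, and the TLS dose-limiting toxicity rule leans on them

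*Protocol*

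**What the plan says.** **Prophylaxis.** Section 17.1.10.10.1 (TLS Prophylaxis) states that "TLS prophylaxis is mandatory for all infusions", as set out in Table 16. Footnote o to Table 4 (Part A Schedule of Activities) begins "All participants will receive TLS prophylaxis during the intra-patient ramp up", adds monitoring over the first 24 hours in the same sentence, and goes on: "this requirement will continue until they have received at least one AZD4573 dose at the target dose level". The matching footnote to Table 5 (Part B) says the same. Section 17.1.10.10.3 repeats the ramp-up scope: "All patients will receive TLS prophylaxis during the intra-patient ramp up". Table 16 gives allopurinol from 3 days before AZD4573 and "continuing at least through the end of Week 1", and its footnote b says that it should not then be stopped.

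**Admission.** For participants with TLS during ramp up, Section 4.1 first strongly recommends admission for further administrations. It then says: "Participants who have previously experienced TLS should be admitted the night before each AZD4573 dose for TLS prophylaxis". Section 17.1.10.10.3 says: "Admitting the patient for subsequent dose administrations will be done at Investigator discretion". Section 8.2.10, which like Section 4.1 is core text, carries the same sentence. Neither makes an exception for earlier TLS.

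**DLT definition.** Section 15.3 counts Grade 3 or higher clinical TLS "that occurs despite protocol-recommended management will be considered a DLT". Laboratory TLS counts if it has not resolved within 5 days despite that management. Section 15.3 also makes any Grade 3 or higher non-haematological toxicity a DLT, with listed exceptions. TLS is not among them.

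**The concern.** TLS is an important identified risk for AZD4573, and prophylaxis is one of the main safeguards against it. A site working from the Schedule of Activities and a site working from Section 17.1.10.10.1 could treat the same participant differently once the target dose has been reached. Two sites could also handle admission differently for a participant who has already had TLS.

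The statistical interest lies in the DLT count. The clinical TLS criterion depends on what the protocol recommends as management. If that has two readings in Weeks 4 and 5, so may the classification of an event in those weeks, and the mTPI-2 table works with very small numbers.

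**Working it through.** **Where the prophylaxis texts differ.** Under Section 13.1, Cycle 1 has 5 weekly infusions. The ramp up is the first 3 administrations, and the target dose is given in Weeks 3, 4 and 5. On schedule, the first target-level dose is infusion 3.

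| Infusion | Section 17.1.10.10.1 | Tables 4 and 5 footnotes, Section 17.1.10.10.3 |
|---|---|---|
| 1 to 3 | mandatory | given |
| 4 and 5 (DLT window) | mandatory | not stated; the footnote's requirement has lapsed |
| Cycle 2 onwards | mandatory | not stated |

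The open part of the DLT window is 5 − 3 = 2 infusions, both at target dose.

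**Is there a rule that settles it?** The module-over-core rule in Section 5.1 and at the start of Section 14 is written for eligibility criteria. The discrepancy rule in Section 17.1.10.10.1 covers protocol against institutional guidelines, not protocol against itself. The prophylaxis conflict lies wholly inside Module 1, so no core/module ranking could resolve it. On admission, Section 4.1 refers the reader to the modules for TLS management, which leads to Section 17.1.10.10.3, the text in tension with it. Section 8.2.10 is core, so the core also disagrees with itself.

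**Link to the DLT definition.** Section 15.3 does not say which section defines the recommended management. Its one cross-reference for TLS monitoring is to Section 17.1.5, which is headed B Symptoms, and to Appendix F. Two criteria could apply to Grade 3 or higher TLS: the specific one, conditional on management, and the general non-haematological one, which is unconditional. The text does not rank them.

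**How much one event can matter.** Table 11 was rebuilt as mTPI-2 with a Beta(1,1) prior, equivalence interval 0.25 to 0.35, sub-intervals of width 0.10, and DU where P(p > 0.30) > 0.95. It reproduces every printed cell except the four at n = 1 and n = 2 that its own footnotes change to S. With 3 evaluable participants, 0 DLTs gives E, 1 gives S and 2 gives D. With 6, 1 gives E, 2 gives S and 3 gives D. For n = 3 to 9 there are 3 + 4 + 5 + 6 + 7 + 8 + 9 = 42 cells with at least one DLT. Counting one DLT fewer changes the decision in 3 + 3 + 2 + 3 + 3 + 3 + 3 = 20 of them. This shows how sensitive the rule is to a single classification. It does not show that any classification went wrong.

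**The case against.** The strongest reply on prophylaxis is that no passage expressly ends it at Week 3. The footnote belongs to the monitoring row of the schedule, and Sections 8.2.10 and 17.1.10.10.3 restate the same end point with monitoring as the sole subject. Giving prophylaxis during ramp up does not mean giving it only then, and Section 17.1.10.10.1 is the section designated for prophylaxis. This has force. A reader might infer that the protocol stops prophylaxis after Week 3, and the documents do not go that far. What stands is that the footnotes name prophylaxis and monitoring together before referring to one requirement that lapses, and two places give ramp up as the scope.

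On admission, the discretion sentence is general and Section 4.1 is specific to earlier TLS. A strong recommendation can coexist with discretion. An instruction covering every dose cannot easily do so.

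Other inferences a reader might draw are not supported:

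- Allopurinol has a third, conflicting end point. Its Week 1 limit is a minimum, and footnote b says to continue.
- MZL participants with smaller nodes have no prophylaxis. Section 17.1.10.10.2 mandates IV saline for all. Only the antihyperuricaemic regimen and the saline volume are unstated for those outside the Table 16 row.
- The laboratory TLS criterion depends on prophylaxis. It turns on resolution after onset.
- An event without prophylaxis would escape the DLT count. The general Grade 3 or higher rule may capture it.
- The 16/38 (42.1%) in Section 2.2.6 measures the risk at stake. That section lists it as Grade 3/4 TLS and also describes it as laboratory evidence of TLS. The data include an 18 mg target dose, whereas Module 1 stops at 12 mg, where Section 13.3 reports no DLTs of clinical TLS. No rate is given for Weeks 4 and 5.

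Finally, Section 4.1 says that recruitment has stopped, so rewording will not alter future escalation decisions.

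**Conclusion.** The point holds as an inconsistency in two safety instructions and an unclear DLT criterion. It does not show that dose escalation was compromised. The prophylaxis texts can be read differently for infusions 4 and 5 of the DLT window, assuming no dosing delay, and for every infusion from Cycle 2. The admission texts differ for any participant with earlier TLS.

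Two consequences remain live. Existing DLT calls for Grade 3 or higher TLS need a stated basis. Section 15.2 also applies the same criteria beyond Cycle 1, with a trigger at more than 30% of participants. And participants still benefiting may continue AZD4573 under protocol guidance (Section 6.13), with only SAEs followed once the database closes (Sections 4.5 and 15.7). They are likely to be past ramp up, which is where the texts diverge. No number of affected participants or events can be given from the protocol.

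**What to change.** Reconcile Sections 4.1, 8.2.10, 17.1.10.10.1 and 17.1.10.10.3 and the TLS footnotes to Tables 4 and 5 into one statement, and have the other places cite it. It should say:

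- which infusions require prophylaxis, separately from which require 24-hour monitoring;
- which prophylaxis applies to participants outside the Table 16 row, beyond the hydration already mandated for all in Section 17.1.10.10.2;
- what admission requirement applies after a TLS event.

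In Section 15.3, refer to that statement by number as the definition of recommended management, and reconcile the TLS criteria with the general Grade 3 or higher non-haematological criterion so that it is clear which governs.

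The sponsor's clinical team decides which existing rule stands. No new rule for counting DLTs is proposed. The cost is a wording amendment and notice to sites, with no change to data collection or analysis.

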17.1.10.10.2 Management of Hydration

Adequate fluid intake for all patients enrolled into the study is mandatory, in particular, around the times of AZD4573 dosing.

All patients are **mandated** to receive IV fluid hydration with normal saline (NaCl 0.9%). For patients at intermediate or high risk for TLS, normal saline 500 mL should be administered over 2 to 4 hours prior to AZD4573 and then continued at a rate of 100 to 175 mL/h as tolerated to maintain urine output.

In case of diarrhoea/nausea/vomiting, more aggressive IV fluid hydration may be needed as clinically indicated. Patients are also encouraged to drink enough fluid before and after each dosing. Please use diuretics carefully, do not use them prophylactically, only if patients have signs of hyper-hydration.

17.1.10.10.3 TLS Prophylaxis, Monitoring, and Management

Please refer to [Appendix F](#) for definitions of the Howard modification of Cairo-Bishop criteria for clinical and laboratory TLS.

All patients will receive TLS prophylaxis during the intra-patient ramp up and be monitored for TLS during the first 24 hours post start of dose. Monitoring for TLS includes checking potassium, calcium, phosphate, uric acid, and creatinine. Fluid balance must be monitored according to institutional standards.

Patients will be required to be monitored for TLS for up to 24 hours post dose until they have received at least one AZD4573 dose at the target dose level (ie, for at least the first 3 AZD4573 once-weekly doses). If a patient has no signs of laboratory TLS at the 6-hour TLS monitoring assessment, the patient may leave the clinic after the collection of other laboratory samples, as per the SoA, at 7 hours after the start of the infusion and managed as an outpatient, at the discretion of the Investigator. These patients must return to the clinic the next morning to complete the 24 hour TLS monitoring period as per the SoA (Cycle 1 Weeks 1-3). Patients with TLS at the 6-hour TLS monitoring assessment must be admitted for in-patient TLS monitoring for a minimum of 24 hours after the start of the infusion and monitored every 4 to 6 hours during this time (or more frequently if clinically indicated).

Sites retain the option to hospitalise patients based on clinical judgement, despite normal TLS laboratory results 6 hours after the start of the infusion. Admitting the patient for subsequent dose administrations will be done at Investigator discretion.

Any hospitalisation due to occurrence of an AE must be reported as an SAE, per definition. However, if hospitalisation is purely for the purposes of extended observation then this does not qualify as an SAE and does not need to be reported.

For all patients, results of safety laboratory testing (haematology and clinical chemistry at a minimum) must be available within 72 hours prior to dosing and must be reviewed by the Investigator prior to each administration of AZD4573.

In particular, the uric acid level must be < ULN prior to the start of each AZD4573 infusion.

It is strongly recommended that for all patients with elevated uric acid (hyperuricaemia) and intermediate/high risk of TLS, rasburicase (0.20 mg/kg/d IV over 30 minutes) should be administered as prophylaxis prior to AZD4573 and repeated as clinically indicated thereafter as per local standard.

NOTE: If hyperuricaemia is present at Screening and/or during intra-patient ramp up, SoC therapy for hyperuricaemia should be administered (including IV fluid and

rasburicase or allopurinol) to reduce the uric acid levels to < ULN before each administration of AZD4573. Rasburicase and allopurinol must not be co-administered.

Any patient developing laboratory TLS must be treated promptly for electrolyte abnormalities (such as hyperkalaemia) to prevent arrhythmias/seizures and for elevated uric acid (hyperuricaemia) with rasburicase (0.20 mg/kg/d IV over 30 minutes for up to 5 days) to prevent acute renal failure and monitored closely for signs of progression to clinical TLS.

If these measures are inadequate, then haemodialysis represents definitive therapy and should be initiated promptly.

Any patient with hyperkalaemia should receive cardiac monitoring with continuous telemetry for ECG changes associated with potentially life-threatening arrhythmias.

Patients with TLS or suspicion of TLS will remain in hospital to undergo additional investigations until the TLS has resolved.

In patients at high risk of TLS based on high tumour burden/bulky disease (> 10 cm), high proliferation rate (LDH > 2 x ULN), and/or impaired renal function ([Coiffier et al 2008](#)), 24-hour hospitalisation for TLS monitoring is recommended during the intra-patient ramp up.

